## 5. PATIENT ENROLLMENT

All patients will be screened by the study site's principal investigator or one of the study site's sub-investigators prior to entry on this study. An explanation of the study and discussion of the potential risks and benefits will be fully disclosed to the patients prior to the screening process in

order for the patient to provide a voluntary written informed consent. Only eligible and consenting patients will be entered into the study.

The screening period for a patient commences when the patient signs the informed consent form. The consent form must be signed before any study-specific tests are performed.

The IRB / EC of an institution must approve the consent form document to be used at the center prior to its local activation; changes to the consent form during the course of the study will also require IRB / EC notification/approval.

Patients who cannot give informed consent (i.e. mentally incompetent patients, or those physically incapacitated such as comatose patients) are not to be recruited into the study. Patients competent but physically unable to sign the consent form may have the document signed by their legal guardian. Each patient will be provided with a full explanation of the study before consent is requested.

**All participants must be centrally registered through the Central Registration Office within Herbert Irving Comprehensive Cancer Center at CUMC prior to initiation of study treatment.**

Registration hours are available Monday through Friday from 9:00am – 5:00pm EST (excluding holidays and weekends). Same day patient registrations (and after hour registrations) will be accommodated on a case by case basis provided that the study team has expressed all time sensitive registration concerns/cases in a timely manner to the Central Registration Office.

**CPDM Central Registration Procedures:**

Within 48 hours of obtaining consent (excluding holidays and weekends), a completed/signed IRB approved informed consent HIPAA form, and demographics forms must be submitted to the CPDM Central Registration Office via an email to [[contact]](mailto:[contact]) or fax to [contact], with the subject line “AAAR1117 Pending Subject Registration Request (PHI)”. Upon receipt, applicable subject information as well as a “pending eligibility” status will be entered into HICCC’s institutional database. This status will remain until further source documentation is made available to confirm overall patient eligibility. Required materials for all pending registration submissions are as follows:

- Completed/signed IRB approved/stamped Informed Consent Forms, including additional study ICFs (e.g., tissue, DNA, etc.), as applicable.
- The completed/signed IRB approved HIPAA Authorization form
- Completed/signed CPDM ICF checklist
- Completed/signed HICCC personal census form
- Completed/signed CPDM Demographics Note to File

In order to confirm eligibility status, Investigators/designees (e.g., study specific Clinical Research Coordinator/Research Nurse, etc.) must submit the following documentation to the Central Registration Office via email or fax:

- The completed/signed study specific Eligibility Checklist (signed by an Physician level Investigator)
- Copies of source documentation necessary for each item to be verified on the CPDM specific Eligibility Checklist, including but not limited to:
  - Copy of required laboratory test and procedure reports (e.g., hematology, serum chemistry, pregnancy test when applicable, MRI reports, CT/bone scans, etc.)
  - Copy of pathology and surgical reports
  - Copy of clinic note(s) or other appropriate medical records capturing the consent process information, along with providing source documentation of any other items needed for screening/eligibility that are not captured in other source document forms (e.g., positive investigator statements of unique eligibility items not captured via other direct source documentation, concomitant medication lists, etc.)
  - Protocol deviation/waiver approvals (if applicable)
- **Please note:** subject line of email or fax should include the following: “[AAAR1117](#) Complete Subject Registration Request (PHI)”.

Upon receipt of the above mentioned documentation, participant eligibility information will be verified by a qualified Central Registration Registrar. If any questions arise during the review process, queries in the form of emails will be addressed to the applicable study team personnel for clarification prior to enrollment. All applicable finalized registration/eligibility information will then be entered into HICCC’s institutional CTMS database by the Central Registration Registrar.

Upon completion, an official subject registration notification email will be sent to the PI/research team which will include eligibility/enrollment status, as well as subject ID information. Protocol therapy may not be initiated prior to receipt of this notification from the Central Registration Office.

All screen fail/ineligible subjects, as well as subject's who withdraw consent prior to enrollment/initiation of protocol therapy must be submitted to the Central Registration office in a manner analogous to the procedures noted above. Applicable source documentation will be required within the corresponding submissions.

## **6. TREATMENT PROCEDURES**

The responsibility for treatment of patients rests with the individual Investigator. The protocol treatment is to begin within 14 days of the screening visit.

### **6.1 Entinostat Administration**

The starting dose of entinostat will be 5 mg administered orally every week (days 1, 8, 15, and 22) of a 28 day treatment cycle. The dose may be changed from 5 mg weekly to 10 mg every two weeks after cycle 1 for patients who have not experienced treatment-related adverse events (excluding manageable events) with severity grade  $\geq 2$  (moderate). Provisions for dose reductions are described in Section 6.3.

Entinostat is supplied in 5 mg (intense yellow in color) and 1 mg (light brown in color) coated tablets. Study drug should be taken in the morning. Tablets should be taken on an empty stomach, at least 2 hours after a meal and at least 1 hour before the next meal.

Tablets should be taken whole and not crushed. If a patient vomits after taking a dose of medication, dosing should not be re-administered but instead the dose should be skipped. If the patient inadvertently missed the dose on scheduled day, the dose could be taken within 2 days of the scheduled dose. However, all efforts should be made to adhere to dosing schedule.

Procedures for dose reductions and delays due to toxicity are summarized in Section 6.3. In the event of necessary dose reductions, each study site pharmacy will be supplied with 1.0 mg tablets in addition to the 5.0 mg tablets.

Unused tablets or empty bottles will be returned to the clinic for accountability purposes.

## **6.2 Treatment Duration**

Patients who display progressive disease or unacceptable toxicity to treatment will be removed from protocol treatment at the time that event is documented. Further disease management will be at the investigator's discretion. If the patient withdraws from study treatment due to toxicity related to study drug, the patient will be followed until the resolution or conclusion of the event.

All patients will be treated until progression or intolerable toxicities occur.

## **6.3 Dose Adjustments**

**Adverse events** that are classified as unrelated or unlikely related do not require dose adjustment, and the prior dose can be resumed once the **adverse event** has resolved. For toxicities that are classified as possibly related to the AE, dose adjustment should be addressed as follows:

For patients who are escalated to 10 mg every two weeks, any toxicity  $\geq$  Grade 2 will result in an initial reduction to 5 mg every two weeks. If the grade of the toxicity is  $\leq$  grade 2 for all toxicities or  $\leq$  grade 3 for laboratory abnormalities other than hepatic, renal or hematologic, an increase in dose to the prior level can then occur after the toxicity has completely resolved and the 5 mg every two weeks dose has been shown to be tolerable. Patient may then receive either 10 mg every two weeks or 5 mg every week at the discretion of the investigator.

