### 6.3.2 Entinostat-related Hematologic Toxicity

The guidelines in Table 6-2 will be followed for determining the timing of cycles based on hematologic status at the time of planned dosing.

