**Table 6-2 Hematologic Toxicity: Dose Modification for Entinostat**

Toxicity	Dose modifications 
≥Grade 3 neutropenia, ≥Grade 3 uncomplicated thrombocytopenia, or Grade 2 complicated thrombocytopenia	
Administer symptomatic remedies/ start prophylaxis.
 
Hold dose until recovery to Grade 1 or study baseline.
 
 
If not recovered by next scheduled dose, skip the dose. If recovered by next scheduled dose, resume study drug at prior dose.
 
If receiving 2 mg dose, and not recovered by either of the next 2 scheduled doses, permanently discontinue study treatment. Otherwise, skip each dose. If recovered for either of these doses, resume study drug as follows: 
 
If receiving 5 mg, restart study drug at 3 mg.
 
If receiving 3 mg, restart study drug at 2 mg.
 
 
 
If dose is held for 4 consecutive weeks, permanently discontinue study drug.
 

Recurrence of the same hematologic toxicity	
If the same hematologic toxicity recurs:
 
 
Administer symptomatic remedies/ start prophylaxis. If receiving 2 mg, permanently discontinue study drug. Otherwise, hold dose until recovery to Grade 1 or baseline.
 
If receiving 2 mg dose, and not recovered by either of the next 2 scheduled doses, permanently discontinue study treatment. If recovered for either of the next 2 scheduled doses, resume study drug as follows: 
 
If receiving 5 mg, restart study drug at 3 mg
 
If receiving 3 mg, restart study drug at 2 mg
 
 
 
If the same ≥Grade 3 event recurs (i.e., third occurrence) despite entinostat dose reduction to 2 mg, as described above, discontinue study drug.
 

 If Entinostat dose is reduced, an increase in dose to prior level can occur only after the AE has completely resolved.

 If greater than 50% of doses are missed during any 6 week period, discontinue from study drug treatment.

**Please note:** Patients that do not require a dose reduction due to AE during the first treatment cycle should continue at 5mg weekly for at least one more cycle prior to changing to 10mg biweekly.

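### For patients escalated to 10 mg every two weeks, section 6.3 and Table 6-2 give different restart doses after a quickly recovered hematologic event, and no text says which governs

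*Combined protocol and SAP*

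**What the plan says.** Section 6.1 starts everyone at 5 mg weekly and allows an optional change to 10 mg every two weeks in patients without treatment-related events of Grade 2 or higher, manageable events aside. The note under Table 6-2 adds that patients who needed no dose reduction in the first cycle "should continue at 5mg weekly for at least one more cycle prior to changing to 10mg biweekly". The earliest 10 mg dose is therefore on Day 1 of cycle 3.

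Two rules then cover hematologic toxicity in an escalated patient:

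- **Section 6.3** has a paragraph written for these patients. Any toxicity at or above "Grade 2 will result in an initial reduction to 5 mg every two weeks". A return to the earlier level is allowed for toxicity up to Grade 2, or up to "grade 3 for laboratory abnormalities other than hepatic, renal or hematologic, an increase in dose to the prior level can then occur", once the event has fully resolved and the lower dose has proved tolerable.
- **Section 6.3.2** says: "The guidelines in Table 6-2 will be followed for determining the timing of cycles based on hematologic status at the time of planned dosing". The events that this table covers are "≥Grade 3 neutropenia, ≥Grade 3 uncomplicated thrombocytopenia, or Grade 2 complicated thrombocytopenia". Dosing is held until recovery to Grade 1 or baseline, and then: "If recovered by next scheduled dose, resume study drug at prior dose". For slower recovery it says "If recovered for either of these doses, resume study drug as follows", followed by steps from 5 mg to 3 mg and from 3 mg to 2 mg only.

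Footnote 1 to the table reads: "If Entinostat dose is reduced, an increase in dose to prior level can occur only after the AE has completely resolved".

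**The concern.** An escalated patient with, say, Grade 3 neutropenia that recovers before the next dose falls under both rules. Section 6.3 halves the dose. Table 6-2 leaves it unchanged. An investigator who follows one departs from the other.

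What is at stake is patient safety and uniform dosing across up to 4 centers. Section 2.2 lists neutropenia and thrombocytopenia among the most frequently reported entinostat events. Section 11.4 sets no formal safety stopping rule, so the dose-modification rules are a main prespecified protection for the individual patient.

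Three lesser points in the same rules are unclear:

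- Table 6-2 has no line for a patient on 10 mg whose event recovers slowly or recurs, whereas Table 6-1 has one.
- The division of non-hematologic events between section 6.3 and Table 6-1 is uncertain. Section 6.3 speaks of possibly related events, in a lead-in that says related to the adverse event rather than to the drug. Section 6.3.1 limits Table 6-1 to events judged probably or definitely caused by entinostat.
- The 3 mg and 2 mg steps carry no dosing frequency.

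**Working it through.** The protocol states no figure to reproduce here. The check sets the two rules side by side and then works out the dose.

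**1. Do both rules reach the same event?** The Table 6-2 triggers are neutropenia of Grade 3 or higher, uncomplicated thrombocytopenia of Grade 3 or higher, and complicated thrombocytopenia of Grade 2. All meet the section 6.3 threshold of Grade 2. Section 6.3.2 is headed as entinostat-related but names no attribution level, so a possibly related hematologic event falls under both.

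**2. What does each rule give after recovery by the next scheduled dose?**

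| | Section 6.3 | Table 6-2 |
|---|---|---|
| Restart dose | 5 mg every two weeks | prior dose = 10 mg every two weeks |
| Dose per 28 days | 2 × 5 = 10 mg | 2 × 10 = 20 mg |
| Change from 20 mg | 10/20 − 1 = −50% | 20/20 − 1 = 0% |
| Return to 10 mg, Grade 3 or higher | no route stated | immediate |
| Return to 10 mg, Grade 2 | allowed after resolution and tolerability | immediate |

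The fourth row follows because the Grade 3 allowance in section 6.3 leaves out hematologic abnormalities.

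**3. Does other text settle it?**

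- Section 6.1 refers to section 6.3 as a whole, which contains both rules.
- Section 6.3.2 speaks of the timing of cycles, but Table 6-2 is titled as dose modification and prints restart doses.
- Footnote 1 governs increases after a reduction, not whether to reduce. It sets a necessary condition and is compatible with the stricter limits in section 6.3, so it is not part of the conflict.

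**4. Illustration over the interim response window** (first 6 cycles, section 11.4). Assume the first 10 mg dose is on cycle 3 Day 1, Grade 3 neutropenia follows and recovers by Day 15, there is no further event, and there is no re-escalation.

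- Doses from cycle 3 Day 15 to cycle 6 Day 15: 1 + 2 + 2 + 2 = 7.
- Section 6.3: 7 × 5 = 35 mg.
- Table 6-2: 7 × 10 = 70 mg. Ratio 70/35 = 2.0.

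This assumes detection between the scheduled Day 1 and Day 15 tests. If the event is found on Day 15 and dosing resumes on cycle 4 Day 1, six doses remain: 6 × 5 = 30 mg versus 6 × 10 = 60 mg, again two-fold.

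**5. Non-hematologic events, if split by attribution.** A possibly related Grade 2 event leads to 2 × 5 = 10 mg per 28 days until re-escalation. A definitely related Grade 4 event restarts, after the hold, at 5 mg weekly: 4 × 5 = 20 mg per 28 days. The less certain and milder event would get the larger, though reversible, cut.

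**The case against.** The strongest reply is that ordinary reading resolves the conflict. Section 6.3 has the only paragraph addressed to escalated patients, and it calls its cut an initial one. Every dose named in Table 6-2 starts at 5 mg, which suggests the table was written for patients on that dose. On this view section 6.3 brings the patient down first and Table 6-2 applies afterwards. This is a sensible reading and probably the intended one. It remains an inference: section 6.3.2 says without qualification that Table 6-2 is to be followed, and the prior-dose branch excludes nobody.

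Safeguards and limited reach also count:

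- Restart comes only after recovery to Grade 1 or baseline, at a dose the protocol permits, and section 7.2 requires blood results to be reviewed before the next dose.
- Section 2.2 says Grade 3 and 4 hematologic abnormalities are much less prevalent in solid tumors.
- Escalation is optional and restricted, in a trial of at most 40 patients.
- Under section 6.3 few patients on 10 mg would reach the recurrence row, so that gap is small.
- The 35 versus 70 mg illustration takes the earliest possible escalation and event and treatment through cycle 6. It is an upper case, not a typical one.

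All of this stands and limits the weight of the point. The attribution and frequency questions are missing detail and do not carry it; the allowance of up to 3 missed doses in 4 weeks in Table 6-1 does suggest weekly dosing. None of it removes two instructions that cannot both be obeyed.

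**Conclusion.** The concern holds. For an escalated patient whose Table 6-2 event recovers by the next scheduled dose, the protocol prescribes both 5 mg and 10 mg every two weeks, a two-fold difference (10 versus 20 mg per 28 days), and states no precedence. After a Grade 3 or higher event the difference can last, since section 6.3 gives no route back to 10 mg. After Grade 2 complicated thrombocytopenia it can be temporary.

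This should be fixed as a matter of dosing safety and consistency. The number of patients affected is not given in the protocol and is not estimated here. No effect on the objective response rate is claimed and no design figure changes; section 11.5 defines evaluability without regard to dose level.

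**What to change.** Amend the wording as follows:

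1. In Table 6-2, limit the prior-dose branch to patients who are not on 10 mg every two weeks.
2. In both the first-event and recurrence rows, add a line for 10 mg every two weeks that restarts at 5 mg every two weeks, matching section 6.3.
3. State that the re-escalation limits in section 6.3 apply in addition to footnote 1.
4. State in section 6.3 whether it or Table 6-1 governs non-hematologic events, by attribution, and correct the lead-in so that relatedness refers to entinostat.
5. Give the dosing frequency for the 3 mg and 2 mg steps, including the step down from 5 mg every two weeks.

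If the sponsor wants 10 mg resumed after quick hematologic recovery, write that exception into section 6.3 in place of item 1, and limit the line in item 2 to slower recovery and recurrence.

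The cost is a short protocol amendment, with no extra patients, visits or procedures.

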**Table 6-1 Non-hematologic Toxicity: Dose Modifications for Entinostat**

Toxicity	Dose modifications
Grade 4	
Administer symptomatic remedies/ start prophylaxis.
 
Hold dose until recovery to Grade 1 or baseline under the following directions.
 
 
1. If recovered within 4 weeks of onset (i.e.: ≤3 missed doses) , resume study drug as follows: 
 
• If receiving 10 mg bi-weekly, restart study drug at 5 mg weekly.
 
• If receiving 5 mg, restart study drug at 3 mg
 
• If receiving 3 mg, restart study drug at 2 mg
 
• If receiving 2 mg, discontinue study treatment
 
 
 
2. If dose is held for 4 consecutive weeks, permanently discontinue study drug.
 

Grade 3	
Administer symptomatic remedies/ start prophylaxis. Hold dose until recovery to Grade 1 or baseline under the following directions:
 
 
1. If not recovered by next scheduled dose, skip the dose. If recovered by next scheduled dose, resume study drug at prior dose or per investigator's discretion.
 
2. If not recovered by either of the next 2 scheduled doses and receiving 2 mg, permanently discontinue study treatment. Otherwise, skip each dose and if recovered by the 4th dose, resume study drug as follows: 
 
• If receiving 10 mg bi-weekly, restart study drug at 5 mg weekly.
 
• If receiving 5 mg, restart study drug at 3 mg.
 
• If receiving 3 mg, restart study drug at 2 mg.
 
 
 
3. If dose is held for 4 consecutive weeks, permanently discontinue study drug.
 

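### For patients escalated to 10 mg every two weeks, section 6.3 and its tables order different doses after the same drug-related toxicity, and nothing says which rule governs

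*Combined protocol and SAP*

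**What the plan says.** Section 6.1 starts everyone on 5 mg weekly, permits a change to 10 mg every two weeks in patients free of treatment-related events of Grade 2 or higher (manageable events excluded), and refers to section 6.3 as a whole for dose reductions.

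**Section 6.3 text.** Events "classified as unrelated or unlikely related do not require dose adjustment". For possibly related toxicity in an escalated patient, any event at or above "Grade 2 will result in an initial reduction to 5 mg every two weeks". A return upward is allowed for events of Grade 2 or lower, or up to "grade 3 for laboratory abnormalities other than hepatic, renal or hematologic, an increase in dose to the prior level can then occur", once the event has fully resolved and the reduced dose has proved tolerable. Then: "Patient may then receive either 10 mg every two weeks or 5 mg every week at the discretion of the investigator".

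**Table 6-1 (non-hematologic; probably or definitely related, per section 6.3.1).** For Grade 3 and Grade 4: "Hold dose until recovery to Grade 1 or baseline under the following directions". After Grade 4, slow-recovering Grade 3 or recurrent Grade 3: "If receiving 10 mg bi-weekly, restart study drug at 5 mg weekly". For a first Grade 3 event that clears quickly: "If recovered by next scheduled dose, resume study drug at prior dose or per investigator's discretion". For Grade 2 or lower, interruption is at the investigator's discretion, in consultation with the medical monitor, and the original dose is resumed on resolution.

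**Table 6-2 (hematologic; no attribution tier stated).** Dosing is held. If the patient has recovered by the next scheduled dose, step 1 resumes the prior dose. For slower recovery or recurrence, only the steps from 5 to 3 mg and from 3 to 2 mg are listed; there is no 10 mg line.

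**The concern.** Section 6.3 and the tables are each written as instructions to be followed, and they give an escalated patient different doses for the same event. With up to four centers, the dose after a drug-related toxicity would depend on which part of section 6 the site reads.

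Two things are at stake. The first is patient protection: section 11.4 sets no formal safety stopping rules, so the individual dose rules carry much of that burden. The second is the consistency of exposure and safety data among escalated patients, safety being a secondary objective.

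**Working it through.** The plan gives no figure to reproduce. The check is a comparison of the texts plus the planned dose over a cycle.

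**Inputs.** A cycle is 28 days with weekly dosing on days 1, 8, 15 and 22 (section 6.1). That is 4 doses when weekly and 2 when every two weeks.

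**Formula.** Planned dose per 28 days = mg per dose × number of doses.

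- 10 mg every two weeks: 10 × 2 = 20 mg.
- 5 mg weekly (Table 6-1 restart): 5 × 4 = 20 mg; (20 − 20)/20 = 0%. Each single dose falls from 10 to 5 mg.
- 5 mg every two weeks (section 6.3): 5 × 2 = 10 mg; (10 − 20)/20 = −50%.

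**Side by side, for a patient on 10 mg every two weeks (planned mg per 28 days):**

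| Event | Section 6.3 | Table |
|---|---|---|
| Grade 4 non-hematologic, recovered within 4 weeks | 10, no return provided | 6-1: 20 (5 mg weekly) |
| Grade 3 non-hematologic, slow recovery or recurrent | 10; return only for laboratory abnormalities other than hepatic or renal | 6-1: 20 (5 mg weekly) |
| Grade 3 non-hematologic, recovered by next dose | 10 | 6-1: prior dose or discretion, so compatible |
| Grade 2 non-hematologic | 10 first, return later | 6-1: 20 (original dose) |
| Grade 3 neutropenia, recovered by next dose | 10, no return provided | 6-2 step 1: 20 (prior dose) |
| Grade 3 neutropenia, slower recovery | 10 | 6-2: no 10 mg line |

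In the Grade 2 row it does not matter whether the original dose means 10 mg every two weeks or 5 mg weekly. Both total 20 mg, and section 6.3 places both after a period on 5 mg every two weeks.

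**Can the rules be applied in sequence?** No. Section 6.3 reaches 5 mg weekly only as an increase, and Grade 4 is outside its return limits. Table 6-1 orders that dose as the immediate restart.

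**Does attribution separate them?** If possibly related and probably or definitely related events are treated as separate classes, a possibly related Grade 2 event cuts the planned 28-day dose by 50%, while a definitely related Grade 4 event cuts it by 0%. The less certain drug effect would get the larger planned cut. The split also leaves Table 6-2 unresolved: it has no tier, while section 6.3 covers any toxicity and names hematologic abnormalities in its return rule.

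**Comparison with a never-escalated patient.** After the same Grade 4 event, a patient on 5 mg weekly goes to 3 mg. If weekly dosing is kept (assumption), that is 3 × 4 = 12 mg; (12 − 20)/20 = −40%. After the same quickly resolved Grade 3 neutropenia, that patient resumes 20 mg.

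**The case against.** The best defence is scope. Section 6.3 introduces its rule with possibly related toxicities and section 6.3.1 confines Table 6-1 to probable or definite ones, so read literally the two do not cover the same events. The text permits that reading, but it gives the implausible ordering shown above and does nothing for Table 6-2.

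Several further points stand and limit the concern:

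- **Table 6-2's missing 10 mg line** might be read as another contradiction. It is a gap, and the section 6.3 rule for escalated patients can fill it. Only step 1 of that table clashes.
- **A reduction that raises the dose.** The tables say "If receiving 5 mg, restart study drug at 3 mg" without an interval. A reader might infer that a patient on 5 mg every two weeks (10 mg per 28 days) would move to 3 mg weekly, 3 × 4 = 12 mg, or +20%. That needs a change of interval that nothing in the documents orders. Keeping the interval gives 3 × 2 = 6 mg, or −40%.
- **Holding.** It is tempting to say that every such patient is first held until recovery. That is so in the Grade 3 and Grade 4 rows of Table 6-1 and in Table 6-2, but at Grade 2 in Table 6-1 interruption is discretionary.
- **Harm.** A reader might infer that the Table 6-1 restart is unsafe because the 28-day total does not fall. Each single dose is halved, and nothing in the documents shows whether single dose or 28-day dose drives toxicity.
- **Reach.** Escalation is optional. A note under both tables asks for at least one more cycle at 5 mg weekly after cycle 1 before changing.

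**Conclusion.** The inconsistency is real. For escalated patients, two sets of mandatory instructions cannot both be followed after Grade 4, slow-recovering Grade 3 or recurrent Grade 3 non-hematologic toxicity, after Grade 2 non-hematologic toxicity, or after Grade 3 or higher neutropenia or thrombocytopenia that has recovered by the next dose. In each case the planned dose is 10 mg per 28 days on one reading and 20 mg on the other.

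This rests on taking the instructions as written and on finding no precedence statement in section 6. It is a statement about planned dose and not a demonstrated difference in toxicity. The number of patients exposed cannot be estimated, because the documents give no expected number escalated.

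It would be wrong to carry the point over to the efficacy conclusions. The objective-response decision rule and sample size do not involve these dose rules, and section 11.5 counts completed cycles whatever the dose level.

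**What to change.** Amend section 6.3 and both tables as follows:

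1. State in section 6.3 which rule governs for patients on 10 mg every two weeks, and that it covers possibly, probably and definitely related events.
2. Use one step-down dose from 10 mg in section 6.3, Table 6-1 and Table 6-2. Of the two existing choices, 5 mg every two weeks is the stricter.
3. Make the Grade 2 or lower row of Table 6-1 and step 1 of Table 6-2 agree with that rule, and add a 10 mg line to Table 6-2.
4. State whether the discretion in Table 6-1 for a quickly recovered Grade 3 event is kept.
5. Keep each table's own hold and discontinuation rules, including discretionary interruption at Grade 2.
6. As a clarification, state that steps to 3 mg and 2 mg keep the patient's current dosing interval.

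The change is to protocol wording only. If 5 mg every two weeks is chosen, some escalated patients will receive a lower planned dose after a brief event: 10 mg instead of 20 mg per 28 days, half of what a never-escalated patient resumes after the same quickly resolved Grade 3 neutropenia. Writing in a conditional return to 5 mg weekly, once the event has resolved and the reduced dose is tolerated, limits that cost.
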